DSMRC	Defence Services Medical Research Centre, Myanmar Ministry of Defence	OCRA	Office of Clinical Research Affairs, DMID, NIAID, NIH, DHHS
ERC	Ethics Review Committee	OHRP	Office for Human Research Protections
FWA	Federal-Wide Assurance	ORA	Office of Regulatory Affairs, DMID, NIAID, NIH, DHHS
GCP	Good Clinical Practice	PI	Principal Investigator
GMS	Greater Mekong Sub-Region	RDT	Rapid diagnostic test for malaria
HIPAA	Health Insurance Portability and Accountability Act	RIP	Research information portal

List of Abbreviations

icddr, b	International Centre for Diarrhoeal Disease Research, Bangladesh	sFTP	Secure file transfer protocol
ICF	Informed Consent Form	SMC	Safety Monitoring Committee
ICH	International Conference on Harmonisation	SOP	Standard Operating Procedure
IEC	Independent or Institutional Ethics Committee	usPCR	Ultrasensitive polymerase chain reaction
IRB	Institutional Review Board	WHO	World Health Organization

PROTOCOL SUMMARY

Title:	Preliminary Study of Subclinical Malaria
Population:	Up to 6,000 residents of all ages in villages, refugee camps, military bases, and work sites, including children, pregnant women, and the elderly; the number of participants screened to achieve enrollment ceiling is not known
Number of Sites:	Up to 6 (each with at least 2 villages, towns, unions, refugee camps or plantations, or a single military base)
Study Duration:	Up to 1.5 years
Subject Duration:	Up to four months (military population may be under observation up to 4-6 weeks)
Ethical Oversight:	Ethics Review Committee (ERC), Department of Medical Research (DMR), Myanmar Ministry of Health and Sports (MoHS) Institutional Review Board (IRB), Defence Services Medical Research Centre (DSMRC), Myanmar Ministry of Defence IRB, International Centre for Diarrhoeal Disease Research (icddr,b), Bangladesh IRB, National Institute of Parasitic Diseases (NIPD), Chinese Center for Disease Control and Prevention (China CDC) IRB, Duke University Health System

Study Objectives:**Primary objective:**

Make a preliminary assessment of the dynamics of subclinical malaria detected by ultrasensitive PCR to guide the design of a matched cohort study of subclinical malaria in Myanmar and along its borders with China and Bangladesh

(The objective of the subsequent matched cohort study, to be reviewed as a separate protocol, will be to compare the incidence of clinical malaria and malaria transmission capacity, in participants with and without subclinical malaria.)

Secondary and exploratory objectives:

1. Within usPCR+ and usPCR- cohorts, test for association between demographic and other risk factors (e.g. occupation, travel) and incidence of clinical malaria and transmission capacity
2. Collect preliminary data to estimate the history of exposure to malaria parasite and mosquito vector species by serological profiling
3. Collect preliminary data to develop a model system to predict future malaria risks using geospatial and satellite data on environmental conditions, patterns of parasite migration and human mobility, field data on vector abundance and malaria burden over time at study sites

2. BACKGROUND INFORMATION AND SCIENTIFIC RATIONALE

2.1. Background Information

2.1.1. Malaria, antimalarial drug resistance, and malaria eradication

Malaria is caused by a mosquito-borne, protozoan parasite belonging to the genus *Plasmodium*. Of the five species of *Plasmodium* that infect humans, *P. falciparum* and *P. vivax* are responsible for the majority of morbidity and death. The malaria burden is greatest in sub-Saharan Africa, with a high mortality in children under five years of age. In Asia, malaria endemicity is lower, but it presents a major public health problem, affecting people of all ages due to a lack of the acquired immunity that can be developed through the continuous, heavy exposure more typical of Africa. *P. falciparum* is susceptible to genetic polymorphisms associated with antimalarial drug resistance, and Southeast Asia has been the epicenter of repeated emergences of drug resistant malaria [1]. Malaria can be cured completely if treated with effective drugs. Artemisinin-based combination therapies (ACTs) are the first line malaria treatment globally. The widespread implementation of highly efficacious ACTs has contributed to large reductions in the malaria burden in many parts of the world, inspiring a renewed hope of global malaria eradication [2].

2.1.2. Myanmar is the frontier of artemisinin resistance and a crucial battleground for malaria elimination

Southeast Asia has become a focus in the war against malaria after the emergence of artemisinin resistant falciparum malaria. Myanmar, the emerging democracy formerly known as Burma, has the heaviest malaria burden in the region, with more cases and deaths than the rest of the region combined [3]. Artemisinin resistance first emerged in Cambodia [4-6] and has been documented by us and others along the borders of Myanmar with Thailand [7, 8] and China [9], in central Myanmar, and in southern Laos and southern Vietnam [10]. Although artemisinin resistance is manifested chiefly by delayed parasite clearance so long as the ACT partner drug is effective, with the new emergence of resistance to ACT partner drugs treatment failure now occurs in up to 46% of people treated with ACTs in western Cambodia [11], raising the specter of untreatable malaria, and threatening prospects for eradication [12]. The populations currently impacted by artemisinin resistance are those living in the six Greater Mekong Sub-Region (GMS) countries: Cambodia, Vietnam, Laos, Thailand, China's Yunnan Province, and Myanmar (Figure 1). Importantly, Myanmar shares borders with Bangladesh and India, two countries with no evidence yet of confirmed artemisinin resistance, but both with large populations at risk of malaria and travel links to Africa.

Figure 1. Map of the Greater Mekong Subregion.

The initial response to artemisinin resistance was to try to contain it by eliminating falciparum malaria from western Cambodia and erecting a “firewall” to block its spread. The containment strategy, led by the World Health Organization (WHO), the Global

Fund to Fight AIDS, Tuberculosis and Malaria, and regional governments, was predicated on the assumption—based on past patterns of spreading drug resistance—that a “wave” of resistance was spreading westward from Cambodia toward Myanmar [10]. The Myanmar Artemisinin Resistance Containment zone was launched along the Thailand-Myanmar border where diagnosis, treatment and prevention were scaled up [13] and pilot mass drug administration (MDA) schemes were implemented from across the border in Thailand into Myanmar’s Kayin [14], as well as in Mon and Tanintharyi States (unpublished).

Using genomic epidemiology approaches, we recently demonstrated that while artemisinin resistant parasites have indeed spread between Cambodia and southern Vietnam, the resistant parasites initially present in Myanmar emerged *de novo* there [15]. This unexpected finding—which was immediately shared with Myanmar’s National Malaria Control Program (NMCP), other country partners, and the WHO—challenged the notion that erecting a firewall along Myanmar’s eastern border could stop the spread of resistance: if resistance can pop up independently, it will be impossible to contain. An urgent technical expert review [16] led the WHO to abandon the containment strategy and to instead launch a regional malaria elimination campaign [17, 18]. Myanmar endorsed the goal of malaria elimination by 2030 at the East Asia Summit in November 2015, and a costed national malaria elimination plan for Myanmar was finalized in 2016.

2.2. Scientific Rationale

2.2.1. Risks of Asymptomatic or Subclinical Malaria

Myanmar’s NMCP currently stratifies malaria risk at the township level, based on ecological risk factors for malaria transmission, reported clinical cases, and presence of or proximity to artemisinin resistance. This stratification scheme, though practical, does not account for heterogeneous malaria risk or distinguish between locally acquired and imported malaria, resulting in inefficient targeting of interventions. Moreover, malaria elimination may require eradicating all parasites from all infected persons, not just those with clinical symptoms [19]. If clinical malaria represents the “tip of the iceberg”, understanding the rest of the iceberg—whether it poses risk or even benefit to infected individuals, and how it contributes to transmission in different epidemiological settings—will be important for malaria control and elimination.

“Asymptomatic”—or more accurately, *subclinical* malaria—has long been recognized in semi-immune Africans [20]. New “ultrasensitive” molecular tests [21-23] have recently revealed unexpectedly high rates of subclinical malaria in Southeast Asia, where long held dogma had it that all infections quickly give rise to symptoms in presumably non-immune people. Some argue that “asymptomatic” infections are both harmful and infectious and must be treated [24]. The WHO recently endorsed MDA for malaria elimination in Southeast Asia [18], and increasingly large scale MDA schemes are being undertaken based on subclinical malaria prevalence as measured by ultrasensitive tests [14]. However, no previous studies have assessed the clinical risks or transmission potential of the extremely low-density malaria infections detected by these tests.

Using an ultrasensitive reverse transcription polymerase chain reaction (usPCR) assay that we developed [22], we are finding that the prevalence of malaria at sites within and bordering Myanmar is highly heterogeneous. Villages with high prevalence—including some MDA sites—are often in close proximity to villages with little or no malaria. While our usPCR test

reliably detects *P. falciparum* and *P. vivax* at parasite densities below 16 parasites/mL, these very low-density infections are difficult to further characterize using currently available molecular and *in vitro* methods, precisely because the parasite densities are so low—up to 10,000-fold lower than those detected by rapid diagnostic tests (RDTs) and ten to 100-fold lower than conventional PCR (Figure 2).

Clinical risk or benefit. A recent review concluded that “asymptomatic malaria” is a chronic and debilitating condition that should be treated” [24]. However, most of the cited studies of “asymptomatic” or subclinical malaria infection used microscopy or rapid diagnostic tests for malaria (RDTs), which have lower limits of detection (LoD) of about 100 parasites/ μ L (or 10^5 /mL). More recently studies have used standard PCR, with an LoD of about 1000-5000 parasites/mL [25]. In contrast, a high-volume intravenous usPCR assay has an LoD of 22 parasites/mL [21] and the LoD of a finger-stick assay that we developed and are using (Figure 2) is <16 parasites/mL [22]. Although studies are conflicting as to whether subclinical malaria at parasite densities detected by conventional methods is protective or harmful [26, 27], no previous studies have assessed the clinical risks or transmission potential of ultralow density subclinical malaria infections.

The ability to detect these ultralow parasite densities is unprecedented, and for the first time it will be possible to study how long these infections last and whether they increase the risk of clinical malaria illness in the infected individual. Alternatively, ultralow density malaria infection could represent a co-adaptation of host and parasite that minimizing symptoms [28].

Transmission potential. It has been argued that malaria elimination requires eradicating all parasites from all infected persons, not just those causing symptoms [19]. Subclinical malaria has been known to be a transmission reservoir in Africa since the 19th century [20, 29], and 40 years ago surveys in Bangladesh found up to 47.3% of people of all ages to be infected with falciparum and/or vivax malaria at the end of the transmission season. These studies used microscopy to detect much higher parasite densities than those detected along the Thailand-Myanmar border by usPCR to guide MDA [14, 23, 28]. Ongoing MDA to eliminate ultralow subclinical malaria is predicated on the assumption that extremely low density infections contribute meaningfully to transmission. It may seem reasonable to assume that any infection is potentially transmissible, but several studies (summarized in [24]) have shown that transmissibility falls with declining parasite density.

There is no evidence at present that ultralow subclinical malaria infections contribute significantly to transmission. Skeptics about the value of MDA in Southeast Asia rightly point out that malaria has been eliminated from many regions without detecting or treating submicroscopic infections, much less ultralow density infections. Despite strong advocacy for MDA by prominent malaria thought leaders [30], scaling up of this controversial but potentially promising intervention is stalled in Southeast Asia as NMCPs await clear answers about the

[figure not shown]

Figure 2. Representation of density of malaria infections detected by our finger-stick usPCR (left), standard PCR (center) and RDTs (right). Black dots represent lower limit of number of parasites detected in an equal volume of blood.

optimize transmission while

clinical and transmission risks posed by subclinical—and especially ultralow density—malaria infection. This study is designed to provide these clear answers.

Study impact. The results of the longitudinal matched cohort study that this pilot study will lead to will influence national and regional malaria control and elimination policies. Whether or not the results of the cohort study support scaling up MDA, the development of robust, highly sensitive surveillance tools will enhance the ability to map and track malaria, capabilities that become increasingly critical as countries approach elimination. Our results may support “targeted MDA” based on microstratification at the village level, a new concept just now gaining currency.

2.2.2. Dynamics of Asymptomatic or Subclinical Malaria Identified by Ultrasensitive PCR

It is well known that many asymptomatic infections may persist for from weeks to months [31-33]. Persistent chronic cases of malaria infection in the absence of new exposure has been described [34]. A recent paper extensively reviewed the nature and dynamics of asymptomatic malaria and its clinical and transmission impact in different transmission zones [35]. However, most of these studies were conducted in areas of high malaria transmission, and used standard methods such as microscopy or RDTs LoDs far higher than that of usPCR. Studies that used sensitive molecular methods in low transmission regions [36, 37] are limited to cross-sectional surveys, and do not assess the dynamics or chronicity of these low-density infections. The natural dynamics of low density malaria infections in humans is unknown; although it has been suggested that these may be chronic infections, their duration has not been described.

2.2.3. Parasite population structure and migration

There is an urgent push for malaria elimination in the GMS, driven by fear of the spread of ACT-resistant malaria. Information on how parasites are migrating, where they come from and where they end up (i.e. “sources” and “sinks”), could help to guide elimination interventions. Recent studies of *P. falciparum* whole genome sequences from the GMS identified highly structured *P. falciparum* populations clustering into multiple distinct genetic subpopulations [38, 39], some of which are associated with artemisinin resistance. Some *P. vivax* populations show similar patterns of population structure and diversity [40], while others show *P. vivax* to be more diverse and less structured than *P. falciparum* [41, 42]. Further studies employing genome sequencing and genome-wide genotyping linked to ecological, epidemiological and geospatial information about risk of exposure to malaria parasite and mosquito vector species have the potential to lead to new tools for predicting malaria risk that would aid in elimination efforts.

2.2.4. Serosurveillance: tracking the parasite’s footprints

Serological tools can be used to map malaria risk [43] and assess time-dependent malaria exposure [44]. Protein microarrays are used to measure antibody responses to large numbers of malaria proteins, including both polymorphic vaccine antigens [45] and variant surface antigens associated with immune evasion and pathogenesis [46, 47]. These microarrays may prove most useful as surveillance tools to detect recent or remote exposure to specific parasite species, life cycle forms, antigenic variants, and even mosquito vectors. Unlike commercially available protein microarrays [44, 48], which measure seroreactivity to hundreds of proteins, each derived from the reference genome, our diversity-reflecting arrays contains dozens to

hundreds of variants of important polymorphic antigens derived from sequencing many hundreds of field isolates. We hypothesize that breadth of recognition of antigen variants will provide a simple and robust way to estimate malaria exposure history in a population. Moreover, mosquito salivary antigens elicit serological responses in humans [49] that can correlate with exposure [50], and we hypothesize that we will be able to estimate exposure to different mosquito vectors by measuring antibodies against species-specific variants of mosquito proteins. We hope to use this information to target malaria interventions more efficiently based on which human populations are exposed to which vectors, e.g. indoor-biting versus forest-biting species.

2.2.5. Mapping and forecasting malaria risks using geospatial and satellite data

Understanding malaria risk as it varies over time and space is essential for effective targeting of interventions. Changing malaria pattern can be understood using two major transmission pathways, namely human and mosquito. Vector ecology likely dominates in determining individuals' risk of exposure at the local scale, because environmental factors largely control mosquito population dynamics and distribution. However, human mobility plays a more significant role at a regional scale as human flow allows for "import" and "export" of local parasite subpopulations, accelerating the dissemination of drug resistance and other heritable traits. The data generated through this study will be used to develop spatially explicit and temporally dynamic approaches to track, monitor, and forecast malaria risk within Myanmar and along its borders with China and Bangladesh, using satellite and geospatial data to aid malaria control and elimination. Earth-observing satellite systems acquire data characterizing environmental conditions and ecosystem states that are routinely used in habitat and risk modeling applications in ecological studies and management applications. At a regional scale, studies of movement paths or trajectories of populations are starting to improve our understanding of the role of human mobility in spreading infections [51, 52]. We will develop highly dynamic depictions of environmental factors in the study areas, including meteorological metrics, landscape matrix, and land use drivers derived from satellite imagery to model local scale parasite abundance and transmission potential.

2.3. Hypotheses

This preliminary study is largely descriptive. The subsequent matched cohort study will test the hypothesis that individuals harboring persistent chronic subclinical *P. falciparum* and/or *P. vivax* parasitemias are protected from clinical malaria, but represent a source of malaria transmission.

2.4. Choice of study design

This is a short longitudinal preliminary study that aims to describe the dynamics of low-density subclinical malaria to support the final study design of a subsequent matched cohort study. To provide the rationale for the current protocol, both studies are described below; a separate protocol for the matched cohort study will be finalized based in part on results of this preliminary study.

2.4.1. Preliminary study

In this study, a small number of asymptomatic infections detected by ultrasensitive PCR (usPCR) will be followed and tested intensively for three months to measure the temporal dynamics of these infections. A much larger number of uninfected individuals will be followed

for just 2-4 weeks (two visits), providing a comparator group for the infected cohort. The validity of our results in a subsequent matched cohort study depends, in part, on our ability to accurately classify infection status using a single usPCR result. In other words, do we have sufficient confidence in the correct classification of malaria infection positive and negative status using usPCR test at the beginning of the study? While there is no gold standard test more sensitive than usPCR, repeated usPCR testing offers a surrogate. Presumably, in a low transmission setting, someone who is truly uninfected on the first testing should remain negative on multiple consecutive tests, but this remains to be confirmed.

If this initial evaluation confirms that usPCR results are relatively stable - i.e., that most usPCR+ infections remain positive on most or all repeated testing over the course of three months, and that most usPCR- infections remain negative upon re-testing 2-4 weeks later, then we can move forward with the cohort study with confidence that our initial classification of exposure is a meaningful basis for assessing subsequent outcomes. If, however, a single usPCR result is found to be "unstable", we may need to consider testing at least twice before assigning infection status. Similarly, we may wish to increase the sample size if we determine that the sensitivity and specificity of a single usPCR test (compared to results of multiple testing) is high enough to proceed with single testing at screening and enrollment, but lower than ideal (e.g. sensitivity/specificity 50-75%).

2.4.2. Design of the subsequent matched cohort study (to be submitted for ethical review later as a separate protocol)

To provide the rationale for this preliminary study, the design of the subsequent matched cohort study is described briefly here. The principle design will be a matched cohort study. This choice of study design is based on the knowledge of generally low prevalence of malaria in most of the proposed study sites. Although a standard cohort study would be appropriate in a high transmission setting, it would be difficult, if not impossible, to reach adequate sample size in our study sites with such low prevalence. A retrospective case control design is also unsuitable, since it will not be possible to measure the exposure of interest (prior subclinical malaria) at the time that the primary outcome (RDT+ infection) is detected. Therefore, a matched case-cohort design similar those we have previously done in Mali [53] offers a good alternative to study a rare exposure.

Matching is not typically used in cohort studies because it precludes testing for association between matched variables and outcomes of interest. However, in this situation, independent association between clinical protection and transmission risk needs to be understood. Because subclinical infection is itself likely to signify higher malaria exposure risk, comparing rates of RDT+ infections and transmission capability in unmatched infected and uninfected cohorts would likely show that clinical malaria and transmission capacity are more common in the infected cohort simply because their initial infection signals greater malaria exposure. Therefore, for the subsequent cohort study we will match infected participants (cases) to uninfected controls, to control for covariates known and suspected to be associated with malaria risk. With this design, we will still be able to test for association with matched variables and outcomes of interest within (but not between) infected and control cohorts.

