3. OBJECTIVES AND OUTCOMES

Primary objective:

Make a preliminary assessment of the dynamics of subclinical malaria detected by ultrasensitive PCR to guide the design of a matched cohort study of subclinical malaria in Myanmar and along its borders with China and Bangladesh

(The objective of the subsequent matched cohort study, to be reviewed as a separate protocol, will be to compare the incidence of clinical malaria and malaria transmission capacity, in participants with and without subclinical malaria.)

Secondary and exploratory objectives:

1. Within usPCR+ and usPCR- cohorts, test for association between demographic and other risk factors (e.g. occupation, travel) and incidence of clinical malaria and transmission capacity
2. Collect preliminary data to estimate the history of exposure to malaria parasite and mosquito vector species by serological profiling
3. Collect preliminary data to develop a model system to predict future malaria risks using geospatial and satellite data on environmental conditions, patterns of parasite migration and human mobility, field data on vector abundance and malaria burden over time at study sites

Primary outcomes:

1. Proportion of individuals with initially positive usPCR tests that were followed by 1 or more consecutive positive tests on weekly or biweekly testing
2. Proportion of individuals with initially negative usPCR tests that subsequently had at least one usPCR positive test at a second screening 2-4 weeks later.

Primary endpoints:

Not applicable

Secondary and exploratory outcomes:

Infection outcomes and endpoints

1. Incidence of falciparum malaria infection by RDT
2. Incidence of vivax malaria infection by RDT
3. Incidence of mixed falciparum/vivax malaria infection by RDT
4. Incidence of falciparum malaria infection by usPCR
5. Incidence of vivax malaria infection by usPCR
6. Incidence of mixed falciparum/vivax malaria infection by usPCR

Serology endpoint

Seroreactivity to polymorphic malaria/mosquito proteins

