4. STUDY DESIGN

4.1. Overview

- Prospective, multi-site short longitudinal study
- Up to six study sites, each with >2 villages, towns, unions, refugee camps or plantations, or a single military base. Alternative and additional sites may be added to ensure enough infected cases.
- Screening for eligibility (age at least 0.5 year; able & willing to strictly follow study protocol and to provide written informed consent or assent as appropriate)
- Enroll and consent eligible individuals
- RDT-positive: one-time enrollment for data and venous blood collection; Refer to and ensure appropriate treatment by care providing team; No study-related follow up
- RDT-negative: Collect data and DBS samples; Return to research clinic in 2-4 weeks
- PCR-negative participants: One follow up visit approximately 2-4 weeks after enrollment
- PCR-positive participants: Five follow up visits at approximately 4, 6, 8, 10, and 12 weeks (for those with total 12 weeks follow up) or 2, 3, 4, 5 and 6 weeks (for those with total 6 weeks follow up) after enrollment
- Total up to 6000 residents in up to six study site of all ages in villages, refugee camps, military bases, and work sites are to be enrolled
- Finger stick blood sampling will be done for RDT and dried blood spot sampling in all participants at each scheduled and unscheduled visit.
- Venous sampling will be done for participants with RDT+ infections detected at times when study staff trained for venous sampling are present. Blood volumes at any time point are limited to 2 mL for children aged < 3 years, 3 mL for age 3-5 years, and 5 mL for older children and adults.
- Estimated duration of study: 18 months

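### Section 7.4 fits the Markov model to monthly steps, but visits are 4, 2 or 1 weeks apart and the spacing differs between the military and other participants

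*Combined protocol and SAP*

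**What the plan says.** Section 7.4 plans Markov-chain models, fitted by maximum likelihood, to find factors that change the probability of moving between usPCR states. It describes the sampling points as monthly. The same section's primary analysis refers to biweekly testing, and Section 3 has initial positives "followed by 1 or more consecutive positive tests on weekly or biweekly testing".

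The visits are set out in Section 4.1, Tables 2a and 2b and Section 6.1.3:

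- "PCR-positive participants: Five follow up visits at approximately 4, 6, 8, 10, and 12 weeks" on the 12-week schedule, and weeks 2, 3, 4, 5 and 6 on the 6-week schedule. Section 6.1.3 assigns the shorter schedule to the military population.
- "PCR-negative participants: One follow up visit approximately 2-4 weeks after enrollment". Table 2a places this visit at week 4 and Table 2b at week 2.

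A secondary objective in Section 3 is, within the usPCR+ and usPCR- cohorts, to "test for association between demographic and other risk factors (e.g. occupation, travel"), so occupation is a named factor.

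Section 2.4.1, in the rationale, also raises the case where "the sensitivity and specificity of a single usPCR test (compared to results of multiple testing) is high enough to proceed with single testing" but "lower than ideal (e.g. sensitivity/specificity 50-75" per cent), as a reason for a larger later cohort. Neither Section 7.1 nor Section 7.4 lists sensitivity or specificity as an outcome or analysis.

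**The concern.** A transition probability has meaning only for a stated length of time. The model is described with one step length, while the data come with three, and the mix differs between the two schedules. Because the weekly schedule is the military one, a difference in step length lines up with occupation and site, which the model is meant to examine. A schedule indicator would not remove the problem: if only the military are on the shorter schedule, that indicator is the military indicator.

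The estimated persistence of infection would also be distorted. Describing these dynamics to guide the matched cohort study is the primary objective.

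**Working it through.** **The plan's own counts.** One screening test plus five follow-ups gives 6 observations for initial positives; one plus one gives 2 for initial negatives; 0.75 × 1,000 = 750 usPCR- per site. All three match Section 7.2.

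**Gaps.** Weeks 0, 4, 6, 8, 10, 12 give 4, 2, 2, 2, 2. Weeks 0, 2, 3, 4, 5, 6 give 2, 1, 1, 1, 1. One of five steps is about monthly on the first schedule and none on the second.

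**Reading 1: each visit is one step.** Assume a constant clearance hazard, the same in both groups, with no reinfection and no test error. The documents give no clearance rate, so the 4-week probability m is an assumption and is varied. With m = 0.20:

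- Hazard = -ln(0.80)/4 = 0.0558 per week. Clearance is 1 - 0.80^0.5 = 0.1056 over 2 weeks and 1 - 0.80^0.25 = 0.0543 over 1 week.
- 12-week schedule: expected clearances 1 - 0.80^3 = 0.488; expected steps at risk 1 + 0.800 + 0.716 + 0.640 + 0.572 = 3.728; per step 0.488/3.728 = 0.131.
- 6-week schedule: expected clearances 1 - 0.80^1.5 = 0.284; expected steps at risk 1 + 0.894 + 0.846 + 0.800 + 0.757 = 4.297; per step 0.284/4.297 = 0.066.
- Odds ratio = (0.131/0.869)/(0.066/0.934) = 2.1, although the true hazards are identical.

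| True 4-week clearance | Per step, 12-week | Per step, 6-week | Spurious odds ratio |
|---|---|---|---|
| 10% | 6.3% | 3.1% | 2.1 |
| 20% | 13.1% | 6.6% | 2.1 |
| 30% | 20.6% | 10.5% | 2.2 |
| 50% | 38.4% | 20.1% | 2.5 |

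The military group would appear to clear more slowly. Allowing 5% acquisition over 4 weeks and weighting the steps equally gives 12.6% against 6.6% at m = 0.20, so the result does not hang on ignoring reinfection.

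Initial negatives are affected in the same way. An assumed acquisition of 5% over 4 weeks is 1 - 0.95^0.5 = 2.5% over 2 weeks, an odds ratio of (0.05/0.95)/(0.0253/0.9747) = 2.0.

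**Reading 2: only intervals of about 4 weeks are used.** The 12-week schedule keeps three non-overlapping steps (0-4, 4-8, 8-12) and leaves weeks 6 and 10 unused. The 6-week schedule keeps one, with four of its five follow-up visits unused. Initial negatives retested at week 2 contribute none.

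**Secondary note: reference status.** Let s be true sensitivity, with persistent infection, independent tests, no false positives, five retests for initial positives and one for initial negatives. Apparent sensitivity of the first test is:

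- any positive, first test counted: 1/(2 - s);
- majority of retests: q/(q + 1 - s), where q is the probability of at least 3 positives in 5;
- first retest only: s.

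At s = 0.60: 1/1.40 = 71%; q = 0.683, so 0.683/1.083 = 63%; and 60%.

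**The case against.** **On the time step.** Section 7.4 does not say that each visit is one equal step, and a maximum-likelihood Markov model can take actual intervals. A competent analyst may well do so, in which case the odds ratio of 2.1 never arises. That stands: a reader might infer that the model will be biased, and the text does not show that. What it shows is a step length that fits one of ten scheduled gaps, with no statement of how the others are handled.

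The calculation also treats lost positivity as real clearance. If it were wholly detection error in persisting infections, the loss per visit would be 1 - s whatever the gap, and the spurious odds ratio would be 1. The 2.1 therefore applies to true changes of state.

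**On sensitivity and specificity.** A reader might go further and infer that the plan's assessment of the single test is broken, because with an any-positive reference 1/(2 - s) cannot fall below 50% and a poor test would pass. The documents do not support that. They never state an any-positive rule; the sentence is rationale for a separate later protocol, in tentative terms; and the 50-75% band is an example. The nearest wording is whether "most usPCR+ infections remain positive on most or all repeated testing over the course of three months". Read as a majority rule, true 50, 60 and 75% become 50, 63 and 78%, and true 30% becomes 19%. At true 30%, only 16% of initial positives would have at least 3 of 5 retests positive, so this check would flag the test. The companion check, that "most usPCR- infections remain negative upon re-testing 2-4 weeks later", is weak: at true 30% it still passes, with 97% staying negative if 250 of 6,000 are usPCR+ and 77% if a quarter are.

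Nor is the first retest shown to be the right reference. It returns s only if infections persist, which is what the study must find out. With an assumed clearance of 3 or 6% per week on the 12-week schedule, a true 75% reads 0.75 × exp(-0.12) = 66.5% or 0.75 × exp(-0.24) = 59% as the share of initial positives positive at the first retest, against 75% or 72% under a majority rule. The first retest also falls at week 2 on one schedule and week 4 on the other.

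**Conclusion.** The mismatch in Section 7.4 is real and needs no assumption to see: the stated monthly step disagrees with the visit schedule and with the biweekly testing named in the same section. Its consequence is conditional. If visits are treated as equal steps, identical clearance in the two schedules appears as an odds ratio of about 2.1 to 2.5 for 4-week clearance of 10 to 50%, under a constant hazard without test error, and aligned with military status. If only monthly intervals are kept, two of five follow-up visits are lost on one schedule and four of five on the other.

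The point is minor. The study is largely descriptive, and the two primary proportions do not depend on the Markov model.

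The absence of a reference rule in Section 2.4.1 is a note for the design of the later cohort, not an error in an analysis this plan contains.

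**What to change.** In Section 7.4, replace the monthly step with the actual visit intervals: either a continuous-time Markov model on recorded visit dates, or interval length as a term in the transition model. State which is used, and tabulate observed transitions by interval length and schedule, so that loss of positivity that does not grow with the interval can be seen. The cost is a sentence or two and modest programming, with no extra visits, samples or data.

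If a single-test sensitivity or specificity is to inform the later cohort, add to Section 2.4.1 the rule that makes a participant reference-positive or reference-negative. Say that initial negatives have one scheduled retest, and show the result under more than one rule. No single rule, including the first retest, should be presented as the correct reference.
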